- a. Hypertension detected in two separate readings during up to three consecutive visits
- b. Well-controlled blood pressure defined as SBP ≤140 mm Hg and DBP ≤90 mm Hg in two separate readings during up to three consecutive visits.
- c. Escalation of trametinib to previous dose level can be considered if BPs remain well-controlled for 4 weeks after restarting of trametinib. Approval from Study Chair is required.
- d. Symptomatic hypertension defined as hypertension aggravated by symptoms (e.g., headache, light-headedness, vertigo, tinnitus, episodes of fainting) that resolve after the blood pressure is controlled within the normal range

I. Dose Modification for **QTc Prolongation and Valvular Changes**

Dose Modification for QTc Prolongation

QTc Prolongation ^a	Action and Dose Modification
• QTcB ≥501 msec	 Interrupt study treatment until QTcB prolongation resolves to grade 1 or baseline. Test serum potassium, calcium, phosphorus and magnesium. If abnormal, correct per routine clinical practice to within normal limits.
	Review concomitant medication usage for agents that prolong QTc.
	 If the event resolves, restart study treatment at current dose level^b. If the event does not resolve, permanently discontinue study treatment. Consider evaluation with cardiologist. If the event recurs, permanently discontinue study treatment. Consider evaluation with cardiologist.

Abbreviations: msec = milliseconds; QTcB = QT interval on electrocardiogram corrected using the Bazett's formula

- a) Based on average QTc value of triplicate ECGs. For example, if an ECG demonstrates a prolonged QT interval, obtain two or more ECGs over a brief period, and then use the averaged QTc values of the three ECGs to determine if study treatments should be interrupted or discontinued.
- b) If the QTc prolongation resolves to grade 1 or baseline, the subject may resume study treatment if the investigator and CTEP medical monitor agree that the subject will benefit from further treatment.

Dose modifications for valvular changes		
Asymptomatic, moderate regurgitation or stenosis by ECHO (Grade 2 mitral/tricuspid/aortic valvular toxicity per CTC AE v4.0)	 Hold study therapy. Repeat ECHO within 1 week, and every 1-2 weeks for 4 weeks. If abnormality recovers within 4 weeks, resume study therapy with one dose level reduction. For such subjects, continue ECHO monitoring 2 and 4 weeks after rechallenge, then every 4 weeks for 12 weeks and then per protocol. If no recovery by 4 weeks, discontinue the study drug. Follow up with echocardiogram as above 	
Grade 3 or 4 (symptomatic, severe regurgitation/stenosis by imaging, with symptoms controlled by medical intervention)	 Permanently discontinue GSK2118436. Continue echocardiogram every 4 weeks for 16 weeks or until resolution. 	

Resumption of the study agent may be considered in patients who were benefiting and have recovered from the valvular toxicities, but would require approval by the study sponsor (CTEP) and study chair)

m. Dabrafenib or Dabrafenib-Trametinib Dose Modification for **Diarrhea**

Episodes of diarrhea have been observed in patients receiving dabrafenib, trametinib, or both therapies in combination. Other, frequent causes for diarrhea including concomitant medications (e.g., stool softeners, laxatives, antacids, etc.), infections caused by *C. difficile* or other pathogens, partial bowel obstruction, etc., should be clinically excluded.

Dabrafenib or Dabrafenib-Trametinib Treatment Modification and Management Guidelines for Diarrhea

Guidelines for Diarrilea		
CTCAE Grade	Management Guideline	ion and Dose Modification
Uncomplicated Diarrhea, ¹ Grade 1 or 2	 Diet: Stop all lactose containing products; eat small meals, BRAT-diet (banana, rice, apples, toast) recommended. Hydration: 8-10 large glasses of clear liquids per day (e.g., Gatorade or broth). Loperamide3: Initially 4 mg, followed by 2 mg every 4 hours or after every unformed stool; maximum 16 mg/day. Continue until diarrhea-free for 12 hours. Diarrhea >24 hours: Loperamide 2 mg every 2 hours; maximum 16 mg/day. Consider adding oral antibiotics. Diarrhea >48 hous: Loperamide 2 mg every 2 hours; maximum 16 mg/day. Add budesonide or other second-line therapies (octreotide, or tincture of opium) and oral antibiotics. 	 Continue study treatment. If diarrhea is grade 2 for > 48 hours, interrupt study treatment until diarrhea resolves to grade ≤1. Restart study treatment at the same dose level.

Dabrafenib or Dabrafenib-Trametinib Treatment Modification and Management Guidelines for Diarrhea

- Calability 101 Digition		
CTCAE Grade	Management Guideline	ion and Dose Modification
Uncomplicated Diarrhea, ¹ Grade 3 or 4 Any Complicated Diarrhea ²	 Clinical evaluation mandatory. Loperamide³: Initially 4 mg, followed by 2 mg every 4 hours or after every unformed stool; maximum 16 mg/day. Continue until diarrhea-free for 12 hours. Oral antibiotics and second-line therapies if clinically indicated Hydration: Intravenous fluids if clinically indicated. Antibiotics (oral or intravenous) if clinically indicated. Intervention should be continued until the subject is diarrhea-free for ≥24 hours. Intervention may require hospitalization for subjects at risk of life-threatening complications. 	 Interrupt study treatment until diarrhea resolves to ≤ grade 1. Restart study treatment reduced by one dose level.⁴ If 3 dose reductions of study treatment are clinically indicated, permanently discontinue study treatment.

- 1. **Uncomplicated diarrhea** defined by the absence of symptoms such as cramping, nausea/vomiting, ≥ Grade 2, decreased performance status, pyrexia, sepsis, neutropenia ≥ Grade 3, frank bleeding, and/or dehydration requiring intravenous fluid substitution.
- 2. **Complicated diarrhea** defined by the presence of symptoms such as cramping, nausea/vomiting, ≥ Grade 2, decreased performance status, pyrexia, sepsis, neutropenia ≥ Grade 3, frank bleeding, and/or dehydration requiring intravenous fluid substitution.
- 3. Loperamide should be made available prior to start of study treatment so loperamide administration can begin at the first signs of diarrhea.
- 4. Escalation of study treatment to previous dose level is allowed after consultation with the medical monitor and in the absence of another episode of complicated or severe diarrhea in the 4 weeks subsequent to dose reduction.

n. Dose Modification for **Visual Changes**

Episodes of visual changes have been observed in patients receiving dabrafenib, trametinib, or the combination of both therapies. An ophthalmologist should be consulted if changes in vision develop. However, if the visual changes are clearly unrelated to study treatment (e.g., allergic conjunctivitis), then monitor closely as it may be reasonable to defer ophthalmic examination.

Uveitis and iritis have been associated with dabrafenib, while RPED and RVO have been associated with trametinib therapy. Monitor patients for visual signs and symptoms (such as change in vision, photophobia, and eye pain) during therapy. Special attention should be given to retinal findings (e.g., retinal pigment epithelial detachment (RPED) or retinovascular abnormalities (i.e., branch or central retinal vein occlusions [RVO]). For events of visual changes regardless of severity but for which an ophthalmic examination is conducted, a blood sample for PK analysis is encouraged when feasible, and the blood sample should be drawn as close as possible to the time of the event.

The ophthalmology exam will include best corrected visual acuity, visual field examination, tonometry, slit lamp biomicroscopic examination of the anterior segment (with special attention to inflammation) and the posterior segment, and dilated indirect fundoscopy with special attention to retinal abnormalities. Optical coherence tomography is strongly recommended at scheduled visits and if retinal abnormalities are suspected. Other types of ancillary testing including color fundus photography, and fluorescein angiography may also be indicated as determined by clinical exam.

Guidelines regarding event management and dose reduction for visual changes considered to be related to study treatment are provided in the table below.

Treatment Modification for Visual Changes

reatment Modification for visual Changes		
CTCAE Grade	Management Guideline	Action and Dose Modification
Grade 1*	Consult ophthalmologist within 7 days of onset.	 If dilated fundus examination cannot be performed within 7 days of onset, hold trametinib until RPED and RVO can be excluded by retina specialist/ ophthalmologist. Dabrafenib may be continued. If RPED and RVO excluded, continue (or restart) trametinib at same dose level If Uveitis/Iritis, refer to table below
		for Iritis/Uveitis If RPED suspected or diagnosed, refer to RPED dose modification table below; report as SAE if diagnosed. If RVO diagnosed: Permanently discontinue trametinib and report as SAE.
Grade 2 and Grade 3	Consult ophthalmologist immediately.	 Hold trametinib. Dabrafenib and GSK2141795 may be continued. If RPED and RVO excluded, restart trametinib at same dose level If Uveitis/Iritis, refer to table below for Uveitis/Iritis If RPED diagnosed, see RPED dose modification table below; report as SAE. If RVO diagnosed: Permanently discontinue trametinib and report as SAE.
Grade 4	Consult ophthalmologist immediately.	Interrupt trametinib. Dabrafenib and GSK2141795 may be continued. If RPED and RVO excluded, may consider restarting trametinib at same or reduced dose after discussion with study medical monitor. If Uveitis/Iritis, refer to table below If RVO or RPED diagnosed, permanently discontinue trametinib and report as SAE.

Abbreviations: RPED = retinal pigment epithelial detachments; RVO = retinal vein occlusion; SAE = serious adverse event

*If visual changes are clearly unrelated to study treatment (e.g., allergic conjunctivitis), monitor closely but ophthalmic examination is not required.

Dose Modification for RPED

Event CTCAE Grade	Action and Dose Modification
Grade 1 RPED (Asymptomatic; clinical or diagnostic observations only)	Continue trametinib with retinal evaluation monthly until resolution. If RPED worsens, follow instructions below.
	 Dabrafenib and GSK2141795 treatment is not affected
Grade 2-3 RPED (Symptomatic with mild to moderate decrease in visual acuity; limiting instrumental ADL)	 Interrupt trametinib. Continue dabrafenib and GSK2141795 Retinal evaluation monthly. If improved to ≤ Grade 1, restart trametinib with one dose level reduction (reduced by 0.5 mg) or discontinue in patients taking trametinib 1 mg daily. If no recovery within 4 weeks permanently discontinue trametinib

Dabrafenib or Dabrafenib-Trametinib Dose Modification for Uveitis and Iritis

Babiaionib et Babiaionib 116	The time Book Mounication for Overtic and Intio
CTCAE Grade	Action and Dose Modification
Uveitis and Iritis	 Continue study treatment Control ocular inflammation with local therapies If not improved to grade ≤1 within 1 week, interrupt dabrafenib until resolution of ocular inflammation and then restart dabrafenib reduced by one dose
	 level If no recovery within 4 weeks, permanently discontinue dabrafenib. Trametinib may continue.

o. Dose Modification for **Pneumonitis**

Pneumonitis has been observed in patients receiving trametinib in combination with dabrafenib. To reduce the risk of pneumonitis, patients will be monitored closely for symptoms, evaluated with imaging and functional tests when appropriate.

	CTCAE Grade
Grade 1	
Grade 2	
Grade 3	
Grade 4	

p. Dose Modification for **Liver Chemistry Changes**

Dabrafenib or Dabrafenib-Trametinib Dose Modification for Liver Chemistry Changes

Dabrateriib of Babrateriib Traffictii	no Dose Modification for Liver Chemistry Changes
Event	Treatment modifications and assessment/monitoring
ALT ≥3x ULN but <5x ULN and TB <2x ULN, without symptoms considered related to liver injury or hypersensitivity and who can be monitored weekly for 4 weeks	 May continue study treatment. Report as SAE if CTEP-AERS reporting criteria is met. If liver chemistry stopping criteria are met any time, proceed as described below.
	MONITORING: Repeat LFT (ALT, AST, ALK, bilirubin) until they return to normal/baseline or stabilise (LFT may be every 2 weeks after 4 weeks if ALT <3x ULN and TB <2 ULN).
 Criteria for discontinuing study drug: When any of the liver stopping criteria below is met, discontinue trametinib and dabrafenib. 1. ALT ≥3xULN and bilirubin ≥2x ULN or >35% direct bilirubin^{1, 2} 2. ALT ≥ 3xULN and INR >1.5, if INR measured² (INR threshold does not apply if subject is on anticoagulant) 3. ALT ≥5x ULN 4. ALT ≥3x ULN persists for ≥4 weeks 	 Immediately discontinue study treatment. Do not restart/rechallenge unless approved by Study Chair. Report as SAE if: 1) CTEP-AERS reporting criteria are met, or 2) patients meet criteria 1-2. Perform liver event ASSESSMENT AND WORKUP (see below). Monitor the subject until liver chemistries resolve, stabilize, or return to baseline (see MONITORING below). If applicable, provide details on required follow up assessments (e.g., follow up for overall survival or disease recurrence or progression). MONITORING: In patients stopping for criteria 1-2 (with abnormal TB
5. ALT ≥3x ULN and cannot be monitored weekly for 4 weeks 6. ALT ≥3x ULN associated with symptoms³ (new or worsening) believed to be related to liver injury or hypersensitivity	 In patients stopping for criteria 1-2 (with abnormal TB and INR, indicating potentially more significant liver toxicities): Repeat liver chemistries (ALT, AST, ALK, bilirubin) and perform liver event follow-up assessments within 24 hours. Monitor subjects twice weekly until LFT return to normal/baseline or stabilize. A specialist or hepatology consultation is recommended. In patients stopping for criteria 2-6: Repeat LFT and perform liver event follow up assessments within 24-72 hours Monitor subjects weekly until LFTs return to normal/baseline or stabilize. ASSESSMENT and WORKUP: Viral hepatitis serology.⁴ If possible, obtain blood sample for PK analysis.⁵ Serum CPK and LDH. Fractionate bilirubin, if total bilirubin ≥2x ULN.

Event	Treatment modifications and assessment/monitoring
(Contd.)	 CBC with differential to assess eosinophilia. Record clinical symptoms of liver injury, or hypersensitivity on AE CRF. Record concomitant medications (including acetaminophen, herbal remedies, other over the counter medications). Record alcohol use.
	 Additional work up for patient stopping for criteria 1-2 (with abnormal TB and INR, indicating potentially more significant liver toxicities): Anti-nuclear antibody, anti-smooth muscle antibody, Type 1 anti-liver kidney microsomal antibodies, and quantitative total immunoglobulin G (IgG or gamma globulins).
	 Serum acetaminophen adduct HPLC assay (in subjects with likely acetaminophen use in the preceding). If there is underlying chronic hepatitis B (e.g. positive hepatitis B surface antigen): quantitative hepatitis B DNA and hepatitis delta antibody.⁶ Liver imaging (ultrasound, MRI, CT) and /or liver biopsy.

Footnotes:

- Serum bilirubin fractionation should be performed if testing is available. If serum bilirubin fractionation testing is unavailable, record presence of detectable urinary bilirubin on dipstick, which indicates direct bilirubin elevations and suggesting liver injury.
- All events of ALT ≥3xULN and bilirubin ≥2xULN (>35% direct bilirubin) or ALT ≥3x ULN and INR >1.5 (if INR measured) may indicate severe liver injury (possible "Hy's Law"). INR measurement is not required, and the threshold value stated will not apply to subjects receiving anticoagulants.
- 3. New or worsening symptoms believed to be related to liver injury (such as fatigue, nausea, vomiting, right upper quadrant pain or tenderness, or jaundice) or believed to be related to hypersensitivity (such as fever, rash or eosinophilia)
- 4. Includes: Hepatitis A IgM antibody; Hepatitis B surface antigen and Hepatitis B Core Antibody (IgM); Hepatitis C RNA; Cytomegalovirus IgM antibody; Epstein-Barr viral capsid antigen IgM antibody (or if unavailable, obtain heterophile antibody or monospot testing); Hepatitis E IgM antibody
- 5. PK sample is desired if feasible. Record the date/time of the PK blood sample draw and the date/time of the last dose of study treatment prior to blood sample draw on the CRF. If the date or time of the last dose is unclear, provide the subject's best approximation. If the date/time of the last dose cannot be approximated OR a PK sample cannot be collected in the time period indicated above, do not obtain a PK sample. Not required for single-dose studies.
- 6. If hepatitis delta antibody assay cannot be performed, it can be replaced with a PCR of hepatitis D RNA virus (where needed) (Le Gal *et al.*, 2005).

q. Dose Modification for **Venous Thromembolism (VTE)**

Event	Dabrafenib	Trametinib (When Used in Combination)
Uncomplicated DVT or PE	Do not modify the dose.	Withhold trametinib for up to 3 weeks. If improved to Grade 0-1, resume at a lower dose level. If not improved, permanently discontinue.
Life Threatening PE	Permanently discontinue dabrafenib	Permanently discontinue trametinib.

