8.0 TOXICITIES TO BE MONITORED AND DOSAGE MODIFICATIONS

8.1 NCI Common Terminology Criteria for Adverse Events

This study will utilize the CTCAE (NCI Common Terminology Criteria for Adverse Events) Version 4.0 for toxicity and Serious Adverse Event reporting. A copy of the CTCAE Version 4.0 can be downloaded from the CTEP home page (http://ctep.cancer.gov). All appropriate treatment areas should have access to a copy of the CTCAE Version 4.0.

- 8.2 General Dose Modification Considerations
 - a. If multiple toxicities are experienced, dose modifications will be based on the toxicity requiring the largest dose reductions.
 - b. No dose escalation or re-escalation is allowed.
- 8.3 Dose Modifications for Dabrafenib, Trametinib, and GSK2141795

The table below outlines the dose levels to be used for any necessary dabrafenib, trametinib and GSK2141795 dose modifications:

Dose Level	Dabrafenib Dose/Schedule
0	150 mg BID
-1	100 mg BID
-2	75 mg BID
-3	50 mg BID

Dose Level	Trametinib Dose/Schedule
0	2 mg QD
-1	1.5 mg QD
-2	1.0 mg QD

Dose Level	GSK2141795 Dose/Schedule
0	75 mg QD
-1	50 mg QD
-2	25 mg QD

Dabrafenib, Trametinib, and GSK2141795 Dose Modification Guidelines

If an AE resolves to Grade 1 or baseline at the reduced dose level, and no additional toxicities are seen after 4 weeks of study treatment at the reduced dose, the dose may be increased to the previous dose level. A dose reduction below 50 mg BID for dabrafenib is not allowed. Dose reduction below 1 mg once daily for trametinib is not allowed. Dose reduction below 25 mg once daily for GSK2141795 is not allowed. However, if dabrafenib, trametinib, or GSK2141795 is permanently discontinued due to an agent specific toxicity (see below), the patient will be allowed to continue on the remaining agent(s).

Study Chair approval is required to restart study treatment after \geq 28 days of dose interruption.

The dose modifications may involve one or both agents, and should be based on the nature, severity and attributions of the AEs. General guidelines are provided in Tables below, with details stipulated in subsequent sections. Study Chair should be consulted if there are questions about the attribution of AEs and how the doses should be modified.

a. Dose Modification for Toxicities **Not Specified** in Subsequent Sections

	T	
CTCAE Grade	Action and Dose Modification	
Grade 1 Grade 2 (tolerable)	Continue study treatment at same dose level (no dose modification).	
	Monitor closely.	

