Subsequent Events:	 Clinical evaluation for infection and hypersensitivity^c Laboratory work-up^c Hydration as required^d Blood sample for cytokine analysis^e Within 3 days of onset of pyrexia: Optimize oral corticosteroid dose as clinically indicated for recalcitrant pyrexia.^g If corticosteroids have been tapered and pyrexia recurs, restart steroids. If corticosteroids cannot be tapered, consult medical monitor. 	 Interrupt dabrafenib. Continue trametinib and GSK2141795. Once pyrexia resolves to baseline, restart dabrafenib reduced by one dose level.^h If dabrafenib must be reduced to <50 mg BID, permanently discontinue dabrafenib.
h Dabrafenib should be reduced by one dose level after three episodes of pyrexia which cannot be managed by best supportive care and increasing doses of oral steroids. Escalation of dabrafenib is allowed if no episode of pyrexia is observed in the 4 weeks subsequent to dose reduction.	_	

c. Dose Modification for **Rash**

Rash is a frequent AE observed in patients receiving trametinib, dabrafenib, and GSK2141795.

The institutional standards for the management of skin-related AEs can differ from these guidelines. In this case, best clinical judgment should be applied and a consultation with the study chair or the CTEP Medical Monitor may be required.

Supportive Care and Dose Modification for Rash

CTCAE Grade	Adverse Event Management	Action and Dose Modification
Supportive care:		

Supportive care:

Prevention:

- Avoid unnecessary exposure to sunlight
- Apply broad-spectrum sunscreen (containing titanium dioxide or zinc oxide) with a skin protection factor (SPF) ≥15 at least twice daily.
- Use thick, alcohol-free emollient cream (e.g., glycerine and cetomacrogol cream) on dry areas of the body at least twice daily.
- Topical steroids and antibiotics should be applied at least twice daily starting on Day 1 of study treatment, to body areas such as face, chest, and upper back.

Use mild-strength topical steroid (hydrocortisone 1% cream) or topical antibiotic (e.g., clindamycin) or oral antibiotics (e.g., doxycycline 100 mg BID, minocycline 100 mg BID)

Action and Dose

2 weeks, interrupt study treatment until recovery to ≤

 Restart study treatment at reduced dose level (all

• Interrupt study treatment until

reduced by one dose level (all

rash recovers to ≤ grade 1.

Restart study treatment

 If no recovery to ≤ grade 2 within 28 days, permanently discontinue study treatment.

grade 1.

agents).3

agents).3,4

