Modification

Supportive Care and Dose Modification for Rash

Adverse Event Management

CTCAE Grade

Grade ≥3

Symptom management:		
Pruritic lesions: cool compresses and oral antihistamine therapies		
 Fissuring lesions: Mo 	nsel's solution, silver nitrate, or zir	nc oxide cream
Desquamation: thick	emollients and mild soap	
 Paronychia: antisepti 	c bath, local potent corticosteroids	s in addition to oral antibiotics; if no
improvement, consul-	t dermatologist or surgeon	
		iven systemic or topical antibiotics
*Rash prophylaxis is rec	ommended for the first 6 weeks of	study treatment
a. * Subjects who deve	lop rash/skin toxicities should be s	seen by a qualified physician and
_	ation for symptomatic/supportive	
Grade 1	Initiate prophylactic and	Continue study treatment.
	symptomatic treatment	If rash does not recover to
	measures.1	baseline within 2 weeks despite
	Use moderate strength topical	best supportive care, reduce
	steroid. ²	study treatment by one dose
	Reassess after 2 weeks.	level (all agents).3
Grade 2	Initiate prophylactic and	 Reduce study treatment by
	symptomatic treatment	one dose level.
	measures.1	 If rash recovers to ≤ grade 1
	Use moderate strength topical	within 2 weeks, increase dose to
	steroid. ²	previous dose level.
	Reassess after 2 weeks.	• If no recovery to ≤ grade 1 within

- 1. Rash prophylaxis is recommended for the first 6 weeks of study treatment.
- 2. Moderate-strength topical steroids: Hydrocortisone 2.5% cream or fluticasone priopionate 0.5% cream.

 Use moderate strength topical steroids PLUS oral methyl-

prednisolone dose pack.2

Consult dermatologist.

- 3. Approval of Study Chair is required to restart study treatment after >28 days of interruption.
- Study treatment may be escalated to previous dose level if no rash is evident 4 weeks after restarting study treatment.
 - d. Dose Modification for palmar-plantar erythrodysesthesia syndrome (PPES)
 - Lifestyle modification: avoidance of hot water, traumatic activity, constrictive footwear, or excessive friction on the skin and the use of thick cotton socks and gloves, and shoes with padded insoles

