Serum creatinine increase >0.2 mg/dL (18 mcmol/L) BUT ≤0.5 mg/dL (44 mcmol/L) above baseline	 Recheck serum creatinine within 1 week. Serum creatinine increase >1 week: contact CTEP Medical Monitor. If elevation persists beyond 4 weeks, recommend evaluation (consider renal biopsy) for etiology; consider nephrology consultation. If pyrexia is present, treat pyrexia as per guidelines.^a 	Continue study treatment at the same dose level.
Serum creatinine increase >0.5 mg/dL (44 mcmol/L) OR >2 mg/dL (>177 mcmol/L)	 Monitor serum creatinine ≥2-times per week. Hospitalization may be necessary if serum creatinine cannot be monitored frequently. If pyrexia is present, treat pyrexia per guidelines. Consult nephrologist if clinically indicated. Perform renal biopsy if clinically indicated, for example: Renal insufficiency persists despite volume repletion. Patient has new rash or signs of hypersensitivity (such as elevated eosinophil count). 	Interrupt study treatment until serum creatinine recovers to baseline. Restart study treatment.b

^a NSAIDs can induce renal insufficiency, especially in patients with dehydration; ;encourage oral fluids or consider IV fluids as clinically indicated. See guidelines for pyrexia Section 6.1.2.

j. Dose Modification for **Reduced Left Ventricular Ejection Fraction**

Decreases of the left ventricular ejection fraction (LVEF) have been observed in patients receiving trametinib. Therefore, ECHO/MUGA must be performed in regular intervals outlined in the Study Calendar. The same procedure (either ECHO or MUGA, although ECHO is preferred) should be performed at baseline and at follow-up visit(s).

^b Investigator may restart at either the same or a reduced dose level. Escalation of study treatment to previous dose level is allowed if another episode of renal insufficiency does not occur after 4 weeks of dose reduction. Consultation with the Study Chair is required before restarting study treatment if there is evidence of thrombotic microangiopathy.

Treatment Modification and Management Guidelines for LVEF Decrease

Clinic	LVEF-drop (%) or CTCAE grade	Dose Modification

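### Section 8.2b bars every dose re-escalation, while 8.3, five of its toxicity notes and 7.3a permit an increase and the Grade 2 rash row directs one; no available text says which governs

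*Combined protocol and SAP*

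**What the plan says.** **The prohibition.** Section 8.2b, under the general dose modification considerations, reads "No dose escalation or re-escalation is allowed". It carries no exception or cross-reference.

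**The permissions.**
- 8.3, general text: once the event has resolved and 4 weeks at the reduced dose have passed without further toxicity, "the dose may be increased to the previous dose level".
- 8.3b, pyrexia, note h: "Escalation of dabrafenib is allowed if no episode of pyrexia is observed in the 4 weeks subsequent to dose reduction".
- 8.3c, rash, note 4: "Study treatment may be escalated to previous dose level if no rash is evident 4 weeks after restarting study treatment".
- 8.3i, renal insufficiency, note b: "Escalation of study treatment to previous dose level is allowed if another episode of renal insufficiency does not occur" after 4 weeks of reduction.
- 8.3k, hypertension, note c: "Escalation of trametinib to previous dose level can be considered if BPs remain well-controlled for 4 weeks after restarting of trametinib", with Study Chair approval.
- 8.3m, diarrhea, note 4: a return is allowed after the medical monitor has been consulted.
- 7.3a (Phase I D+G): patients in a lower cohort can have GSK2141795 raised to the next cohort's level, subject to conditions on the DLT rate and on follow-up.

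**The directive.** The Grade 2 rash row of 8.3c says that if rash recovers to grade 1 or lower "within 2 weeks, increase dose to" the previous level. The introduction to 8.3c qualifies it: "The institutional standards for the management of skin-related AEs can differ from these guidelines. In this case, best clinical judgment should be applied".

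**The concern.** A site that uses any of the permissions breaks 8.2b. A site that obeys 8.2b departs from the Grade 2 rash row as worded. Two sites can therefore treat identical patients differently, and each can point to protocol text in support. In a three-drug combination that is a safety matter.

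There are two consequences for the data. Section 11.4 plans a descriptive summary of the percentage of dose delivered, which would mix the two practices. In Phase I, both routes to DLT evaluability that do not require a DLT (7.3b and 7.4b, item 3) need at least 11 days of GSK2141795 at the assigned dose in Cycle 1. Patients who miss this are replaced. Grade 2 rash is not on the DLT list in 7.3c or 7.4c, so a patient with no other DLT depends on that day count.

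**Working it through.** The plan states no figure on this point, so there is none to reproduce. The textual count is one unqualified prohibition against seven conditional permissions (8.3 general text, five toxicity notes, 7.3a) and one directive.

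**Is there a precedence rule?** Section 7.0 gives a contact for dose modification questions. Section 8.3 refers questions of attribution and modification to the Study Chair. Both are consultation routes. Section 8.3 also says that its tables give general guidelines and that later sections give details. That describes how 8.3 is laid out and does not mention 8.2b. The text between 8.4 and 8.6, where the table of contents places 8.5 (Dose Modification Contacts), was not available and could not be checked.

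**Dose delivered (illustration).** Assumptions: a window of 2 × 28 = 56 days; a denominator of the full assigned dose on all 56 days (11.4 defines neither); full dose before the reduction; reduced dose from Day 15. The reduced dose is a fraction r of full dose. A one-third reduction (r = 2/3) covers dabrafenib 150 to 100 mg, trametinib 1.5 to 1.0 mg and GSK2141795 75 to 50 mg. GSK2141795 50 to 25 mg has r = 1/2.

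Formula: delivered = (full days + r × reduced days) / 56.

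| Case | Re-escalated | Not re-escalated | Gap (points) |
|---|---|---|---|
| General 4-week rule, increase on Day 43, r = 2/3 | (28 + 28 × 2/3)/56 = 83.3% | (14 + 42 × 2/3)/56 = 75.0% | 8.3 |
| Rash row, increase on Day 29, full dose holds, r = 2/3 | (42 + 14 × 2/3)/56 = 91.7% | 75.0% | 16.7 |
| Rash row, second reduction on Day 43, trametinib 1.5 to 1.0 mg | (28 + 28 × 2/3)/56 = 83.3% | 75.0% | 8.3 |
| Rash row, full dose holds, GSK2141795 50 to 25 mg | (42 + 14 × 1/2)/56 = 87.5% | (14 + 42 × 1/2)/56 = 62.5% | 25.0 |
| Rash row, second reduction on Day 43, GSK2141795 50 to 25 mg | (28 + 28 × 1/2)/56 = 75.0% | 62.5% | 12.5 |

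The second-reduction cases arise because the Grade 1 rash row calls for a reduction if rash has not returned to baseline in 2 weeks. Trametinib 1.0 mg and GSK2141795 25 mg are the floors in 8.3, so the patient who was not re-escalated cannot drop further. The gap depends on timing. Within 56 days it vanishes for reductions starting on Day 29 or later under the 4-week rule (29 + 28 = 57), and on Day 43 or later under the rash row (43 + 14 = 57).

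**DLT evaluability.** Let d be the first day of reduced GSK2141795 for Grade 2 rash, with the increase on day d + 14. Days at the assigned dose need not be consecutive.
- Not re-escalated: d − 1 days in Cycle 1, that is 1 to 10 for d = 2 to 11. The 11-day criterion is missed.
- Re-escalated: (d − 1) + (28 − (d + 14) + 1) = (d − 1) + (15 − d) = 14 days. The criterion is met.
- From d = 12, d − 1 is at least 11, so it is met either way.
- The 4-week rules raise the dose on day d + 28, after Cycle 1 ends, so they add no days. The effect comes from the rash row alone.
- At D+T+G Level 1, GSK2141795 starts at its 25 mg floor, so this case does not arise.

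**The case against.** The best defence is that the specific rule displaces the general one: 8.2 is headed as general, and 8.3 says that details follow in later sections. This is an available reading, but the protocol does not state it. It also leaves 8.2b against the opening text of 8.3, which is itself general and covers all three drugs. Nor can 8.2b comfortably be confined to increases above the assigned dose, because it names re-escalation.

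Several limiting points do stand.
- A reader might infer that every one of these rules clashes with 8.2b so that no site can comply. The documents do not support that. The seven permissions are optional, and a site that never increases a dose breaks none of them. Only the rash row is worded as an instruction, and the clinical-judgment clause softens it where institutional standards for skin events differ.
- Hypertension re-escalation needs Study Chair approval, and diarrhea re-escalation needs medical monitor consultation.
- Phase I runs at limited institutions (11.1) with twice-monthly calls (15.2), which may catch divergence. Those calls are directed at trial status and serious toxicities, and a Grade 2 rash need not come up.
- The 16.7 and 25.0 point gaps are best-recovery cases. They should not be read as typical.

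**Conclusion.** The conflict is real, and the wording should be corrected. The prohibition, the permissions and the directive cannot all stand as written, and no available text ranks them.

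Per patient, on the assumptions above, a Day 15 one-third reduction gives a gap of 8.3 points under the general rule. Under the rash row it is 16.7 points, or 8.3 for trametinib 1.5 to 1.0 mg if persistent Grade 1 rash forces a second reduction. For GSK2141795 50 to 25 mg the rash-row gap is 25.0 or 12.5 points on the same two assumptions. In Phase I, a GSK2141795 reduction for Grade 2 rash starting on Days 2 to 11, with recovery by 14 days and no DLT, means an evaluable patient under one rule and a replacement under the other.

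A reader might go further and infer a trial-wide effect or damage to the Phase II design. Neither is supported. The documents give no frequency for these events, the dose-delivery summary is descriptive, and the Phase II sample size and error rates do not depend on which rule governs.

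**What to change.** Reconcile 8.2b with the general text of 8.3, its toxicity tables (including the Grade 2 rash row and the five notes) and the D+G cohort rule in 7.3a, so that one rule governs. Either name the exceptions in 8.2b or remove the conflicting text. Including 7.3a matters: a repair limited to 8.2 and 8.3 would leave 8.2b at odds with it. Whether and when a dose may be raised is the sponsor's clinical decision. The cost is protocol wording only, with no change to sample size or analysis.
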